3.3.2 Methods of minimising bias

We plan to enrol a large enough sample to eliminate random error. Randomisation in 1:1 fashion should reduce any selection bias of patients due to the treating physician's expectation and possible confounders are well distributed among the groups. Randomisation will be done using a CDMS (SecuTrial®) by a trained member of the study personnel. All study personnel will be trained and instructed for the study procedures. The primary outcome evaluation is performed by blinded study personnel via telephone interviews, the primary outcome analysis is performed by our blinded trial statistician not involved the treatment plan of the patients. Other forms of reducing bias will be the use of prospective CRF Forms, the use of validated and commonly applied scores (mRS/NIHSS/GCS/PROMIS®/MOCA) for the outcome assessments and blinded laboratory personnel assessing the biomarker results, as the individuals analysing the biomarkers will have no information regarding the treatment plan of the patient. Lastly, regular quality control will take place to ensure that all procedure standards are met. Explorative stratified sub-group analysis accounting for possible confounders mentioned in 3.2 will be conducted.

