3.3.4 Blinding and Unblinding procedures (Code Break)

Since this is a surgical trial, blinding is not possible for primary care providers. However, the laboratory personnel analyzing the biomarkers as well as the statistician will be blinded as these are not directly involved in the patient care or outcome assessment. Laboratory personnel will be blinded to the allocation as only encoded material will be processed where patients are identified by their patient ID, which gives no hint to the allocation. Likewise, the study statistician responsible for the primary analysis will receive a blinded copy of the data sets. Furthermore, we will conduct blinded outcome assessment at 3 and 6-month follow-up through study personnel blinded to the allocation of the patient in form of a standardized telephone assessment (Appendix 4)[35]. This form of assessment is highly comparable with face-to-face evaluation, is short and easy to implement[36].

Since no patient or care provider blinding is possible (due to the study design including a surgical treatment arm), no emergency unblinding is necessary.

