5.1.4 Interim analysis

As described under “5.1.2.6. Conclusion of sample size estimation”, the data may be inspected any time, but we plan to perform the primary analyses after every 40 patients (20 per arm), and will stop data collection if the BF, in favor of either the null, or the alternative hypothesis is over 10.

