6.6 Amendments

Substantial changes to the study setup and study organization, the protocol and relevant study documents are submitted to the Ethics Committee for approval before implementation. Under emergency circumstances, deviations from the protocol to protect the rights, safety and well-being of human subjects may proceed without prior approval of the Ethics Committee. Such deviations shall be documented and reported to the Ethics Committee as soon as possible.

Substantial amendments are changes that affect the safety, health, rights and obligations of participants, changes in the protocol that affect study objective(s) or central research topic, changes of study site(s) or of study leader and sponsor (ClinO, Art. 29).

A list of all non-substantial amendments will be submitted once a year to the competent EC together with the ASR.

6.7 (Premature) termination of study

The Sponsor-Investigator may terminate the study prematurely according to the following circumstances:

- Arising ethical concerns
- Insufficient participant recruitment
- When the safety of the participants is doubtful or at risk (e.g. when the benefit-risk assessment is no longer positive)

- If alterations in accepted clinical practice that make the continuation of the study unwise arise
- Presence of early evidence of harm or benefit of the experimental intervention

Upon regular study termination, the Ethics Committee is notified via BASEC within 90 days (ClinO, Art. 38).

Upon premature study termination or study interruption, the Ethics Committee is notified via BASEC within 15 days (ClinO, Art. 38).

Biological materials collected until premature termination of the study will be evaluated according to the study protocol as will all acquired data to this point. The study will be published with the data collected until the point of premature termination while mentioning in the publication that a premature termination according to whatever reasons applied was chosen.

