9 MONITORING AND REGISTRATION

Monitoring duties will be provided by the Clinical Trial Unit of the University Hospital Basel. The study site will be initiated with a site initiation visit and then regularly checked during the course of the study as defined in the monitoring plan. All informed consents, source data, e.g. CRF, eCRF and laboratory results, the trial master file and the investigator site file will be monitored. All source data and all documents will be made accessible to monitors and questions will be answered during monitoring through the study staff. The data and safety monitoring committee is independent from the investigator team and consists of an expert in the field, a statistician, a monitor and a data analyst. Additionally, a Patient expert with experience in regulatory affairs will be member of the DSMB, responsible for assessing risk and benefits for the patients during this trial.

This study will be registered in the Swiss National Clinical Trial Portal and in the [Clinicaltrials.gov](https://clinicaltrials.gov) Registry Platform.

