Management and study process	Consulting a patient expert to be part of the data and safety monitoring board and conducting risk-benefit assessment and patient safety aspects within the DSMB.	The patient expert is required to have experience in safety and regulation procedures. The PE is expected to actively participate in the DSMB and faithfully complete his appointed task of assessing risk and benefits for the involved participants.	Ensure patient perspective is taken into consideration for all questions and issues (i.e. safety) that arise during the study. Providing a patient relevant perspective to risks and benefits of the study and potential safety aspects.
Data analysis/Management and study process	As member of the DSMB, the Patient Expert will inadvertently be confronted with results from the regular interim analysis due to the nature of Bayesian modelling. The Patient Expert assesses the risk-benefit ratio according to these results together with the trial statistician	The patient expert is required to have experience in safety and regulation procedures and basic statistic knowledge. The PPI is expected to actively participate in the DSMB and faithfully complete his appointed task together with the trial statistician.	Ensure that important trends in the risk-benefit assessment are detected and that patient safety is maintained in collaboration with the rest of the DSMB.
Dissemination and implementation	Consulting patient an organization representative (i.e. EUPATI-CH or Fragile Suisse) and a caregiver and a patient regarding dissemination and communication of the study results to a broad audience in a patient friendly manner.	The PPI team is expected to collaborate and actively participate in preparing the study results in an appealing and easily understandable fashion together with the study team. The PPI team is required to understand the meaning of the results and its impact on the community they represent.	Ensure that the study results are clear, in lay language and appealing to effectively disseminate them in the relevant population so that the affected patients are addressed and aware of the results
Evaluation	Consulting the PPI Team involved in the study to evaluate the impact of PPIs at different study phases/milestones	The PPIs are expected to attend a debriefing and to actively participate in evaluating the impact of PPI, giving	Gaining important insights into the benefits and the impact PPI had on different phases/milestones of

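### The trial statistician is declared blinded, but Appendix 2 has the trial statistician judge risk-benefit on the interim results, a task that cannot be done blind

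*Protocol*

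**What the plan says.** Four parts of the Protocol describe who analyses what, and with what knowledge of the arms.

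- **Section 3.3.2** lists, among the measures against bias, that "the primary outcome analysis is performed by our blinded trial statistician not involved the treatment plan of the patients".
- **Section 3.3.4** says how: "the study statistician responsible for the primary analysis will receive a blinded copy of the data sets".
- **Appendix 2**, in the row on data analysis and study management, says that "the Patient Expert will inadvertently be confronted with results from the regular interim analysis due to the nature of Bayesian modelling", and continues: "The Patient Expert assesses the risk-benefit ratio according to these results together with the trial statistician". The next column of that row names the trial statistician again as the partner in this task.
- **Section 9** sets up the monitoring committee: "The data and safety monitoring committee is independent from the investigator team and consists of an expert in the field, a statistician", together with a monitor and a data analyst. A patient expert also sits on it.

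Two further sections bear on access. On interim looks, section 5.1.4 states that "the data may be inspected any time, but we plan to perform the primary analyses after every 40 patients". Section 6.7 opens with "The Sponsor-Investigator may terminate the study prematurely according to the following circumstances", and one of the listed circumstances is "Presence of early evidence of harm or benefit of the experimental intervention".

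**The concern.** Surgeons and patients cannot be blinded here, so the protocol relies on the parties who can be: the telephone assessor of the mRS, the laboratory staff and the statistician. Appendix 2 undoes the third of these. The role that sections 3.3.2 and 3.3.4 call blinded is asked to weigh risk and benefit on interim data while patients are still being randomised.

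What is at stake is the independence of choices still open after the first look:

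- how missing primary outcomes are imputed if more than 5% are missing (section 5.2);
- who belongs in the per-protocol set (section 5.1.3);
- how the renewed cost-benefit assessment is made if 200 patients are reached without a decision (section 5.1.2.6).

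A statistician who knows the direction of the effect should not be settling these. A report that describes the statistician as blinded would also be inaccurate if Appendix 2 had been followed.

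**Working it through.** The point concerns roles. The arithmetic only shows what can be done on coded arms and when the blind would lapse.

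**1. Does the stopping test need arm identity?** No. The Bayes factor was recomputed under the logit model of the Bayesian A/B test, with standard normal priors on both parameters. These are taken as the package defaults, which is an assumption because the protocol does not print them.

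- Check against the protocol's own figure (section 5.1.2.5: about 90% of trials reach a Bayes factor of 10 by 70 per arm, at 50% versus 50% × 1.6 = 80%). Simulation gives 90.0% with monitoring after every pair of patients, and 86% for a single look at 70. The stated figure reproduces.
- By 40 per arm, the protocol states 50%. Simulation gives 64% with continuous monitoring and 55% for a single look.
- Swapping the arms: 20/40 versus 32/40 gives ln BF = 2.47 whichever arm is surgery. That is a Bayes factor of about 11.9, above the threshold of 10.

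The numeric stopping rule can therefore be run on arms labelled A and B.

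**2. Does a risk-benefit judgement need arm identity?** Yes, and the same example shows why. The same Bayes factor of 11.9 means benefit if surgery is the 32/40 arm and harm if it is the 20/40 arm. A risk-benefit ratio cannot be formed without knowing which.

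**3. Is it the same person?** Section 3.3.2 calls the blinded analyst the trial statistician, and Appendix 2 uses that title twice for the interim task. Section 9 speaks only of a statistician on an independent committee and does not equate the two. Section 8.1 says that the analysis is done independently by a statistician of the clinical research department and does not mention interim work. Nothing in the Protocol resolves the overlap.

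**4. From when?** Section 5.1.2.6 sets a minimum of 40 per arm before the first test, so 2 × 40 = 80 patients. This is 80/200 = 40% of the maximum. Later looks fall at 120, 160 and 200. With 4,000 simulated trials under the protocol's assumptions, cumulative stopping at the four looks is 56%, 80%, 92% and 97%. About 44% of trials therefore continue past the first look, and more would if the true effect is smaller. Even a trial that stops at 80 has its secondary and sensitivity analyses still to come, because section 5.1.2.6 places them after data collection and follow-up.

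**5. Does recruitment continue around a look?** Assume even accrual over 60 − 6 = 54 months. With 200 patients, 200/54 × 6 = 22 are randomised during any 6-month wait for outcomes. With 150 patients, 150/54 × 6 = 17. So recruitment continues around each look unless it is paused.

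**The case against.** The best defence is that the conflict is one of labels. The Appendix 2 row begins with the patient expert acting as a committee member and ends with the rest of the committee, so the statistician meant may be the committee's own. Section 3.3.4 also uses a different title, the study statistician. This reading is possible and would remove the contradiction, but the text does not state it, and the title used is the one that section 3.3.2 gives to the blinded analyst.

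A second defence is that access to interim data is usually settled in an analysis plan or a committee charter, neither of which is shown. That would excuse silence. It does not excuse two conflicting statements about one role, or an express permission to inspect at any time that is not confined to the committee.

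A third defence is that the consequences are limited, and this largely stands. The mRS is rated by blinded telephone assessors, the threshold is numeric, the imputation trigger is fixed, per-protocol is a sensitivity analysis, and allocation is concealed.

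Three stronger readings are tempting but unsupported:

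- **The Sponsor-Investigator or recruiting team follows the running Bayes factor.** Section 6.7 lists grounds for termination. It does not say that the sponsor sees comparative data, and acting on a committee recommendation fits the same words.
- **About half the patients are randomised by a team that knows the direction.** The sum is 200 − 80 − 22 = 98, or 49%. It needs both disclosure to that team and a run to the maximum. Under the protocol's assumptions, the expected number randomised after the first look is 0.24 × 40 + 0.12 × 80 + 0.08 × 98 = about 27. At the protocol's figure of 150 patients it is 150 − 80 − 17 = 53. None of these is a count of affected patients, because no disclosure is stated.
- **Surgical site infection, recorded in one arm only, unmasks the interim data.** The planned looks are at the primary outcome, and section 5.1.2.6 defers secondary analyses to the end.

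**Conclusion.** The plan is wrong as written: it states a blinding property that its own Appendix 2 contradicts. If followed literally, the trial statistician's blind ends at the first look, at 80 patients, and stays lost for every later look and for the final secondary and sensitivity analyses. This rests on two things: that the shared title means the same person, and that a risk-benefit judgement requires knowing which arm is surgery. The second is secure. The first is what the words say, though the authors may have intended the committee's statistician.

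The permission in section 5.1.4 makes matters worse, since nothing there limits who may look. The size of any bias cannot be computed from the Protocol, and the safeguards above keep it modest for the primary outcome. No sample size or power figure changes. It should be corrected, but it does not undermine the trial's main result.

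**What to change.** - **Sections 3.3.2, 3.3.4, 9 and Appendix 2:** reconcile them so that all arm-identified interim work (direction of the Bayes factor, risk-benefit) is done by the statistician and data analyst already on the monitoring committee. In Appendix 2, name the committee's statistician as the patient expert's partner. State that the trial statistician works on coded arms until the 6-month outcomes are locked.
- **Section 5.1.4:** replace the permission to inspect at any time with the planned looks, and restrict access to comparative results to the committee.
- **Section 6.7:** state that termination for early evidence of harm or benefit follows a recommendation of the committee.

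The cost is protocol and charter wording. No new staff are needed, because section 9 already provides the roles. The one downside is that the sponsor cannot view comparative data between looks.

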Appendix 3 – Patient satisfaction Questionnaire

Questionnaire Patient Satisfaction

[figure not shown]
VISIT 5

Question	Score (1=worst, 5=best)	
1. Did you have the impression that you were well looked after?	 1 point  2 points  3 points  4 points  5 points	 not known
2. Were all of your questions answered properly (i.e. what the further problems of the disease could be, what happens in the future) and did you have the impression that you were taken serious?	 1 point  2 points  3 points  4 points  5 points	 not known
3. Did you have the impression that enough time was allocated for you during your in-patient visit?	 1 point  2 points  3 points  4 points  5 points	 not known
4. How satisfied are you with the treatment outcome (i.e. functional outcome, disability etc.)?	 1 point  2 points  3 points  4 points  5 points	 not known
5. How satisfied are you with your treatment overall?	 1 point  2 points  3 points  4 points  5 points	 not known
Total points		

VISITE 6

Question	Score (1=worst, 5=best)	
1. Did you have the impression that you were well looked after?	 1 point  2 points  3 points  4 points  5 points	 not known
2. Were all of your questions answered properly (i.e. what the further problems of the disease could be, what happens in the future) and did you have the impression that you were taken serious?	 1 point  2 points  3 points  4 points  5 points	 not known
3. Did you have the impression that enough time was allocated for you during your in-patient visit?	 1 point  2 points  3 points  4 points  5 points	 not known
4. How satisfied are you regarding the information received for the future after the trial?	 1 point  2 points  3 points  4 points  5 points	 not known
5. How satisfied are you with your treatment overall?	 1 point  2 points  3 points  4 points  5 points	 not known
Total points		

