Risk / Benefit Assessment	
This study carries relevant risk of death and disability for the included patients due to the underlying disease of SSICH, however if left untreated, outcome may be even worse with a 30-day mortality up to 45% reaching to 54% at one year. The mortality rates however can be attributed almost exclusively to the underlying disease rather than the procedure. Since this is a surgical procedure, risks like bleeding, wound infections, surgical site infection, and complications related to anaesthesiologic procedures may occur. Furthermore, the procedure might, in extremely rare cases, lead to the death of the participant. Also, due to the location of SSICH, important brain structures have to be passed to access the hematoma cavity and, despite all efforts to conserve them, might be damaged.
 
Overall, we acknowledge the possible risk accompanying the proposed surgical method, but it is our opinion that compared with the medical standard of care for SSICH alone or no treatment at all, these risks are acceptable and fairly balanced with the prospect of potential better survival and less morbidity as well as better functional outcome through the proposed surgical method.

Objective(s)	
The primary objective of this two, armed, open-labelled, single centre randomised controlled trial is to show superiority of early minimally invasive image-guided hematoma evacuation additionally to BMT compared to BMT alone in functional outcome rates at 6 months in patients with SSICH.
 
Secondary objectives are:
 
 • to show superior survival rates of patients in the ES arm • to study patient reported quality of life after treatment for SSICH at different time points (3 and 6 months after intervention) • to study patient satisfaction with the outcome after treatment for SSICH at different time points (7 days, 3 months and 6 months after intervention)

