3 STUDY OBJECTIVES AND DESIGN

3.1 Hypothesis, primary and secondary objectives

The **Null hypothesis (H₀)** describes no difference in functional outcome rates of early minimally invasive image-guided endoscopic evacuation additionally to BMT for SSICH compared to BMT alone.

The **Alternative Hypothesis (H₁)** describes a difference (either improved or worsened [two-sided testing]) functional outcome rates of early minimally invasive image guided endoscopic evacuation additionally to BMT for SSICH compared to BMT alone.

The primary objective of this two, armed, open-labelled, single centre randomised controlled trial is to show superiority of early minimally invasive image-guided hematoma evacuation additionally to BMT compared to BMT alone in functional outcome rates at 6 months in patients with SSICH.

Secondary objectives are:

- to show superior survival rates of patients in the ES arm
- to study patient reported quality of life after treatment for SSICH at different time points (3 and 6 months after intervention)
- to study patient satisfaction with the outcome after treatment for SSICH at different time points (3 months and 6 months after intervention)
- to study cognitive outcome in patients after treatment for SSICH at different time points (3 months and 6 months after intervention)
- to study the morbidity rates of patients in both treatment arms
- to study the efficacy of ES in reducing the hematoma volume
- to study the change in focal neurological deficits exhibited by the patients after treatment.
- to study the temporal evolution of serum biomarkers (Neurofilament light-chain subunit (NfL), Glial Fibrillary Acidic Protein (GFAP), S100 calcium-binding protein B (S100B), IL-1 α and β , IL-2, IL-4, IL-5, IL-6, IL-8, IL-10, IL-12p70 and TNF- α) and their change in relation to early hematoma ES.

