3.2 Primary and secondary outcomes

Primary outcome:

- Good functional outcome 6 months after treatment, measured by the mRS[33]. Good functional outcome is defined as a mRS of ≤ 3 points and will be assessed as binary outcome (yes/no, final value) at 6 months after treatment. The cut-off for good functional outcome is chosen at a mRS score of 3 points, as this reflects the turning point for a patient being able to live a partially self-dependent life or to live a severely disabled life. In this context, a mRS score of 3 points reflects the ability to walk unassisted and care for one's own bodily needs despite being moderately dependent on assistance, while a mRS score of 4 points describes a patient who is not able to walk anymore and needs assistance with all daily activities and thus marks a severe loss of patient autonomy.

Secondary outcomes:

- The mortality rate as measured by death of a participant (binary outcome (yes/no), final value) at 6 months after intervention.

- Patient reported outcome measures at 3 and 6 months after intervention, those being:
 - Patient and caregiver quality of life as assessed by the PROMIS® questionnaire (continuous variable, final value)
 - Patient Satisfaction as assessed by a short survey (Appendix 2) on a scale of 1-5 (continuous variable, final value)
 - Patient cognitive outcome as assessed by the MOCA® Test (continuous variable, final value)
- The morbidity rate, meaning occurrence of:
 - Ischemic stroke
 - Recurrent SSICH (defined as any radiologically confirmed increase in hematoma volume postoperative/follow-up that is either asymptomatic or associated with a worsening of the focal-neurological deficit by ≥ 4 points on the NIHSS and/or a decrease in consciousness by ≥ 2 points on the GCS)
 - Epileptic seizure
 - Surgical site infection (intervention group only)
 - Any need for open neurosurgical procedures
 - Infections (i.e. pneumonia, urinary tract infection)
 - Any other not defined complication that prolongs the hospital stay and/or leads to further treatment not envisaged in the original treatment plan.

The occurrence of any of these events 6 months after intervention (binary variable (occurrence/no occurrence), final value, proportion).

- The change of focal neurological deficit measured by the NIHSS, from baseline to 6 months after intervention as a continuous variable (continuous variable, change from baseline).

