4.3.7.2 Questionnaires

The questionnaires used in this study are the Montreal Cognitive Assessment, the PROMIS Scale v1.2 Global Health, and a questionnaire for patient satisfaction derived in our Patient and Public involvement meetings (Appendix 2 and 3). Both, MOCA and PROMIS are well established and validated questionnaires to assess cognition and quality of life respectively and were deemed the most effective and patient friendly by our PPI representatives[39, 40]. Further, the timepoint of assessment was discussed and decided upon with the PPI representatives. The questionnaire regarding patient satisfaction was created together with the PPI representatives by first collecting the most important aspects of patient satisfaction, which were then in a next step condensed to the 5 most important questions. This questionnaire is not validated in clinical trials, but a reflection of important PROMs and a product of intense collaboration with PPIs.

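### The 6-month satisfaction form omits the only question that asks directly about treatment outcome, although the objective is satisfaction with the outcome at 3 and 6 months

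*Protocol*

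**What the plan says.** Section 3.1 gives the objective as "to study patient satisfaction with the outcome after treatment for SSICH at different time points (3 months and 6 months after intervention"). The synopsis has the same objective with a 7-day time point added. Both name the outcome as the object of satisfaction, and both include 6 months.

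Section 3.2 defines the endpoint as "Patient Satisfaction as assessed by a short survey (Appendix 2) on a scale of 1-5 (continuous variable, final value"). Section 4.3.7.2 describes how the questionnaire was made with patient representatives: the aspects that mattered most were collected and then "condensed to the 5 most important questions". That section describes one questionnaire and announces no version specific to a visit. It also says: "This questionnaire is not validated in clinical trials".

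Appendix 3 prints two forms. On the Visit 5 (3-month) form, item 4 reads "How satisfied are you with the treatment outcome (i.e. functional outcome, disability etc".). On the Visit 6 (6-month) form, item 4 reads "How satisfied are you regarding the information received for the future after the trial". The other four items are identical, and item 5 on both is "How satisfied are you with your treatment overall". Each form ends with a line for the total score.

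**The concern.** An objective set for two time points needs an instrument that asks about its subject at both. Here the one question that names the outcome is on the 3-month form only. Six months is also the time of the primary outcome, where a patient's view of the result would naturally be set beside the mRS.

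Scoring rules can be settled later in an analysis plan. An answer that was never collected cannot be. Each patient who completes Visit 6 on the present form is lost for this item.

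There is a second, smaller consequence. The two visits' scores look alike (five items, the same response scale, the same total line) but differ in content. A reader who sees a 3-month and a 6-month result next to each other will tend to take them as repeated measurements of one thing.

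**Working it through.** No sample-size, power or error-rate figure is involved. The check is an item-by-item comparison of the two forms in Appendix 3, followed by arithmetic on the score.

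**Items, Visit 5 against Visit 6**

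| Item | Visit 5 (3 months) | Visit 6 (6 months) | Same? |
|---|---|---|---|
| 1 | Being well looked after | Being well looked after | Yes |
| 2 | Questions answered, taken seriously | Questions answered, taken seriously | Yes |
| 3 | Enough time during the in-patient stay | Enough time during the in-patient stay | Yes |
| 4 | Treatment outcome | Information for the future | **No** |
| 5 | Treatment as a whole | Treatment as a whole | Yes |

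- Items that ask specifically about outcome: 1 of 5 at Visit 5, 0 of 5 at Visit 6.
- Items common to both forms: 4 of 5.
- Item 2, on both forms, already gives what happens in the future as an example of the questions to be answered. Visit 6 therefore touches on future information twice and on outcome not directly at all.

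**Weight of the exchanged item**

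Inputs: five items, each scored 1 to 5 (Appendix 3), all answered.

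- Total: from 5 × 1 = 5 to 5 × 5 = 25, a range of 20 points.
- Four common items: from 4 × 1 = 4 to 4 × 5 = 20.
- Exchanged item: 5 − 1 = 4 points, and 4 / 20 = 20% of the range.
- If the score were the item mean (1 to 5, range 4) instead of the total: 4 / 5 = 0.8 points, and 0.8 / 4 = 20% again.

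So a patient who gives identical answers to the four common items at both visits can still show totals up to 4 points apart because item 4 asks something else. This is a ceiling, not an expected difference. It also assumes complete answers: each item offers a box for not known, and the 5 to 25 range does not hold when that box is used.

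**After the repair**

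With the outcome item asked at both visits, it is available at 2 of 2 visits instead of 1 of 2. With the information question outside the score, 5 of 5 scored items match.

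**The case against.** Several points can fairly be made in the plan's defence.

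- *Item 5 covers the outcome.* In part it may. Satisfaction with treatment overall can reflect how the patient fared, so a reader who infers that the trial collects nothing relevant at 6 months goes too far. But the Visit 5 form asks the two questions separately and so treats them as different. What stands is that no Visit 6 item asks specifically about outcome.
- *The endpoint is broader than the objective.* Section 3.2 speaks of patient satisfaction by a short survey, not of satisfaction with the outcome. Against that wording, Visit 6 does deliver the endpoint. This is correct, and it makes the fault a mismatch between objective and instrument. It does not remove it, because Section 3.1 and the synopsis both name the outcome.
- *The exchange may be deliberate, since Visit 6 is the last visit.* That is possible, as the new item refers to the time after the trial. It remains inference: Section 4.3.7.2 describes a single set of five questions, and nothing gives a reason for dropping the outcome item.
- *No planned test is harmed.* A reader might infer that the comparison of arms at 6 months is biased, or that a treatment effect seen at 3 months would vanish at 6. The documents do not support either. Both arms receive the same form at each visit, the endpoint is the value at the visit, and no test of change from 3 to 6 months is specified. An effect disappearing with the item would require the further assumption that better satisfaction with outcome leaves item 5 unmoved. The four common items can also still be compared across visits.
- *The 1 to 5 scale against a total score.* It is tempting to call this a contradiction. The 1 to 5 scale can describe the single items, and whether they are summed or averaged is a detail that an analysis plan may settle. The point made here does not depend on it.

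**Conclusion.** The point holds in a limited form. As worded, the objective calls for satisfaction with the outcome at 6 months, and the 6-month form has no item that measures it directly (0 of 5, against 1 of 5 at 3 months). The comparison between arms at each visit stays unbiased, but at 6 months it is a comparison of something broader than the stated objective. The 3-month and 6-month totals share four of five items and should not be presented side by side as one measure; the exchanged item accounts for up to 4 of 20 points when all items are answered.

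The consequence is modest. This is one of several secondary outcomes, on an instrument that the protocol itself says is not validated, and the primary outcome, sample size and stopping rule are untouched. It is still worth correcting, because the repair is small and the missing answers cannot be recovered afterwards. The conclusion rests only on the wording of Sections 3.1, 3.2 and 4.3.7.2, the synopsis and the two printed forms.

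**What to change.** Add the Visit 5 outcome question to the Visit 6 form and eCRF. Keep the question on information for the future at Visit 6 as an extra item outside the common score, so that the same five questions are scored at both visits.

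The five-item instrument developed with patient representatives can stay as it is. Replacing it with a single-item endpoint would be a preference and does not follow from the fault. Rewording the objective to general satisfaction would also remove the inconsistency on paper, but it would give up the outcome question at 6 months and leave the two scores unlike each other.

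The cost is one more question at Visit 6 and a small change to the eCRF. For patients already past that visit the item stays missing, and the report should say how many they are.
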